#### 2.1.2 Secondary Objectives and Endpoints

Secondary objectives and endpoints will be assessed from time of start of USB002 or placebo infusion (Visit 1/Day 1) to Day 28.

Secondary endpoints include:

- All-cause mortality at Day 60.
- Number of ventilator-free days (defined as the number of days between Visit 1/Day 1 and Day 28 that subjects are both alive and free of mechanical ventilation [MV]; freedom from MV is further defined as free from MV for at least 48 hours after extubation).
  - In the case of repeated MV, duration of MV will be summed for the purposes of calculation. In the case of tracheostomy, the same criteria apply.
- Proportion of subjects weaned from mechanical ventilation through Day 28 (defined as free from MV for at least 48 hours after extubation. In the case of tracheostomy, the same criteria will apply). This applies only to subjects on mechanical ventilation at baseline.
- Proportion of subjects progressing from non-invasive (at baseline) to mechanical ventilation. This applies only to subjects not on mechanical ventilation at baseline.
- Time to progression (TTP) from non-invasive to mechanical ventilation.

- In the case of repeat admission to hospital and/or ICU within the first 28-days, the time from first treatment with study medication will be used to calculate TTP to MV;
- Number of days of vasoactive agent usage (defined as use of a vasoactive agent for 6 hours or more within any 24-hour period);
- Time (days) to hospital discharge;
- Changes in Ordinal Scale for Clinical Improvement (OSCI) status (see Appendix 1) from Visit 1/Day 1 to Day 28, defined as 1) time to change and 2) proportions of subjects, with 1-point and 2-point clinical status changes utilizing a time-to-event analysis from time of start of infusion (Visit 1/Day 1) of study medication to Day 28 for the time to change analysis between active and placebo groups.

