The secondary efficacy outcomes that are binary, e.g., subjects weaned from mechanical ventilation within the 28-day, subjects progressing from non-invasive (at baseline) to mechanical ventilation, the proportions will be compared using Fisher's exact test. Death will be considered unfavorable outcome for these analyses, i.e. death prior to Day 28 will be considered as on mechanical ventilation. In addition, analysis of subjects weaned from mechanical ventilation will be conducted on those who were on mechanical ventilation at baseline, and analysis of subjects progressing from non-invasive to mechanical ventilation will be conducted on those who were not on mechanical ventilation at baseline. Time to hospital discharge will be analyzed using Kaplan-Meier method. Subjects who are not discharged by Day 28 or die will be censored at Day 28 for the analysis.

All other secondary outcomes will be presented descriptively.

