7.2. Calculated Outcomes

The following are key endpoints derived from data captured at the sites via the EDC system. Complete documentation of the calculations and data manipulation required to go from the CRF database to the analysis database are contained in the companion documents – SDTM Programming Specification File (SDTM Spec) and ADaM Programming Specification File (ADaM Spec).

Outcome	Calculation	Comment
Study Day	= the days from Day 1 (Date of the First Study Infusion) to the event date	
Time in Trial (days)	= Study completion/withdrawal date – date of informed consent date + 1 day	
Time on Treatment	= Date of last infusion – Date of first infusion + 1	
Baseline value	= Value reported prior to the first study treatment	If multiple values collected prior to the first infusion, non-missing value closest to the date/time of the first infusion is considered as baseline value
Change from Baseline	= Value collected at time point (Visit) – Baseline value	
BMI	= $10000 * (\text{Weight in kg}) / (\text{Height in cm})^2$	Value will be rounded to keep one decimal point
Treatment Emergent Adverse Event (TEAE)	= No, if onset date/time AE is before the date/time of the first study infusion = Yes, otherwise	According to conservative rule, all AEs that cannot be determined as started before the first study infusion will be considered as TEAE

Outcome	Calculation	Comment
Time from baseline to achieving $\text{SpO}_2 \geq 94\%$ on room air	= Date of first achieving $\text{SpO}_2 \geq 94\%$ on room air – Date of first infusion + 1 = null if the subject did not achieve $\text{SpO}_2 \geq 94\%$ till study termination	
Number of ventilator-free days	= the number of days between Day 1 and Day 28 that subjects are both alive and free of mechanical ventilation	
Weaned from MV (Yes/No)	= Yes, if the subject was on MV and then weaned from MV through Day 28 = No, if the subject was on MV and kept using MV till Day 28 = null, if the subject did not use MV from Day 1 to Day 28	
Progressed to MV (Yes/No)	= Yes, if the subject progressed from non-invasive (at baseline) to MV on/before Day 28 = No, if the subject was keeping non-invasive till Day 28	
Time to Progression (TPP)	= First MV date – Date of first infusion + 1 = null, if the subject was keeping non-invasive till Day 28	
Time to hospital discharge	= Hospital discharge date – Study Day 1 + 1 = null if the subject was staying in hospital till Day 28	

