8.3.2. Number of ventilator-free days

The number of ventilator-free days (defined as the number of days between Day 1 and Day 28 that subjects are both alive and free of mechanical ventilation) will be summarized by total treatment groups, and by cohort and treatment group, if data applicable.

All Mechanical Ventilation Status data will be listed.

Total MV duration days will be listed and summarized.

8.3.3. Proportion of subjects weaned from mechanical ventilation through Day 28

The number of subjects who were on MV and then weaned from MV through Day 28 will be counted and the proportion of those subjects out of all subjects applied MV will be summarized.

8.3.4. Proportion of subjects progressing from non-invasive (at baseline) to mechanical ventilation.

The number of subjects who progressed from non-invasive (at baseline) to MV will be counted and the proportion of those subjects out of all subjects were not on MV at baseline will be summarized.

8.3.5. Time to Progression (TTP) from non-invasive (at baseline) to mechanical ventilation.

Time to Progression (TTP), i.e., time from first treatment with study medication to MV will be calculated. If enough data applicable, the outcome will be summarized.

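### Ventilator-free days and total MV duration, read alone, can show a subject who died as doing better than a survivor; add a sensitivity row and a split by survival

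*SAP*

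**What the plan says.** Protocol 2.1.2 defines ventilator-free days as the "number of days between Visit 1/Day 1 and Day 28 that subjects are both alive and free of mechanical ventilation", and adds that "freedom from MV is further defined as free from MV for at least 48 hours after extubation". SAP 4.3 repeats both parts. The derivation in SAP 7.2 is "the number of days between Day 1 and Day 28 that subjects are both alive and free of mechanical ventilation", and SAP 8.3.2 uses the same count. Neither SAP derivation restates the 48-hour qualifier, and none of these places gives a death a score of its own.

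SAP 8.3.2 then adds a further output: "Total MV duration days will be listed and summarized". Total MV duration is not in the endpoint lists of Protocol 2.1.2 or SAP 4.3. The protocol sums MV time only as a step in calculating ventilator-free days when ventilation is repeated. No rule says how a death enters this summary.

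Protocol 7.2.1 does contain a death rule. It follows a sentence that begins "The secondary efficacy outcomes that are binary, e.g., subjects weaned from mechanical ventilation within the 28-day", and it reads "Death will be considered unfavorable outcome for these analyses, i.e. death prior to Day 28 will be considered as on mechanical ventilation". The same section sends the remaining secondary outcomes, ventilator-free days among them, to descriptive presentation.

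**The concern.** Both measures depend on how long a subject lived. Ventilator-free days give credit for each day before death that was spent off the ventilator. Total MV duration stops growing at death, so dying early on the ventilator produces a short and apparently favourable value.

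The protocol expects both kinds of subject, since its secondary endpoints separate those on MV at baseline from those who were not. Protocol 6.4.2 also anticipates frequent deterioration among ICU patients and names death from COVID-19 among the expected events. Identifying an early efficacy signal remains a stated objective in SAP section 3, and SAP 7.4 rules out inference, so the descriptive tables are the efficacy readout. If a table of means presents a death as a good result, a reader of that table alone could take the wrong message from it.

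**Working it through.** The documents give no expected ventilator-free days, mortality rate or variance, so there is no planned figure to reproduce. The check applies the written definitions to illustrative subjects over Days 1 to 28.

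Conventions (assumed, because the documents do not fix them): the day of death counts as not alive, and the day of extubation counts as a ventilated day.

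**Ventilator-free days**
- Never-ventilated death on Day *d*: score = *d* − 1. For Day 21, 21 − 1 = 20. Counting the day of death as alive gives 21.
- Survivor with *m* MV days: score = 28 − *m*. Ventilated from baseline and extubated on Day 13: 28 − 13 = 15. Counting Day 13 as unventilated gives 28 − 12 = 16.
- The death outranks the survivor, 20 against 15 (or 16).
- In general the death outranks the survivor when *d* − 1 > 28 − *m*, that is, when *m* > 29 − *d*. For a death on Day 10, 15, 20 or 25, this means survivors with more than 19, 14, 9 or 4 MV days.

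**Total MV duration**
- Death on Day 4 after ventilation from Day 1: 3 days, or 4 if the day of death is counted.
- The survivor extubated on Day 13: 13 days, or 12 if the day of extubation is not counted.
- The death shows the shorter duration.

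**Effect on a group mean**
- SAP section 2 reports 6 + 6 + 6 + 3 = 21 enrolled. The three full cohorts give 3 × 3 = 9 per arm. The split of the last 3 subjects is not stated, so each pooled arm has 9 to 12.
- Scoring one never-ventilated death as 0 lowers the mean by (*d* − 1)/*n*.
- *n* = 10: Day 4 gives 3/10 = 0.3 days; Day 21 gives 20/10 = 2.0 days.
- Day 21, other sizes: 20/12 = 1.7 and 20/9 = 2.2 days. In a single-cohort group of 3, 20/3 = 6.7 days.

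**Would the protocol's death rule change these scores?** Suppose the rule in Protocol 7.2.1 were read day by day, with every day from death to Day 28 counted as ventilated. The Day 21 death would still score 28 − 8 = 20 ventilator-free days, because days after death already earn nothing. Only MV duration would change: the Day 4 death would go from 3 to 3 + 25 = 28 days.

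**The case against.** The strongest reply is that the SAP does what the protocol asks. A reader might infer that the ventilator-free-day count breaks the protocol's own death rule. The documents do not support that: Protocol 7.2.1 ties the rule to the binary outcomes of weaning and progression, and the count matches the definition in Protocol 2.1.2. Nor do the documents contain a zero-for-death score, so adopting one could not be described as restoring consistency with the protocol. This part of the reply stands in full. The SAP 7.2 rows that the rule does govern, weaned from MV and progressed to MV, do not restate it, but that is a separate matter.

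Second, death is not ignored. The count drops every day from death onward, so for a given ventilation course an earlier death can never raise the score. On ventilator-free days the Day 4 death on MV scores 0 against 15, which is the right order. Zero-for-death has its own distortion, since deaths on Day 2 and Day 27 score alike. This is why the protocol count should stay as the defined outcome. It does not help total MV duration, which an earlier death can only shorten or leave unchanged.

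Third, the stakes are low: no inference, deaths listed under SAP 8.3.1, and MV status listed under SAP 8.3.2. The listings let a careful reader reconstruct each case, but they do not alter the summary tables, and the Day 60 death rate is summarised only if the data allow. SAP 7.2 also refers to programming specifications that are not available here and might hold further rules.

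**Conclusion.** The point holds as a limitation of two summaries. It is not a conflict between the documents. For ventilator-free days the limitation is inherited from the protocol; for total MV duration it comes from a summary that the SAP adds. Either measure, read alone, can place a death ahead of a survivor: 20 against 15 ventilator-free days, and 3 to 4 against 12 to 13 MV days, in the cases worked above.

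The effect on a mean depends on the day of death and the group size. In an arm of 10, one never-ventilated death moves it by 0.3 days (Day 4) to 2.0 days (Day 21), and the Day 21 figure ranges from 1.7 to 2.2 days for arms of 12 down to 9. These are illustrations. The documents give no frequency of death without intubation, so they do not show that any such case occurred or that a treatment comparison would reverse. With 21 subjects and descriptive reporting only, the practical consequence is small, but the correction costs almost nothing.

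**What to change.** - Keep the protocol's count of days alive and off MV as the defined outcome in SAP 7.2.
- In SAP 8.3.2, add a second row scoring ventilator-free days as 0 for any death on or before Day 28, labelled as a sensitivity summary that is not in the protocol.
- Summarise total MV duration separately for subjects alive at Day 28 and for those who died, with the number of deaths in the same table.
- Declare these additions in SAP section 6.

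The cost is a few lines of text and programming and one or two extra table rows. The survivor and decedent subgroups will be small, so their summaries should be read next to the listings.

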Respiratory distress in untreated COVID-19 infected patients presents as a progressive continuum from SOB to cardiopulmonary collapse and death. It is diagnosed in symptomatic patients with bilateral lung infiltrates with confirmed positive tests for COVID-19. Without supportive therapy, pulmonary distress rapidly progresses to hospitalization where supplemental oxygen can be given by nasal cannula, high-flow mask, BiPAP mask, and eventually intubation and assisted ventilation. Overall, the physiological damage to cells and structures of the lung can begin within hours of exposure and progress within days (Fahy 2012). The pathologic hallmarks of COVID-19-induced pulmonary distress include neutrophilic alveolitis, hyaline membrane disease secondary to protein transudation and precipitation in the airspace, microthrombi secondary to the generation of procoagulant mediators as well as endothelial and epithelial injury. For these reasons, there is considerable interest in the use of an Angiotensin 1-7 [A(1-7)] to treat patients who have developed respiratory distress from COVID-19 infection (Soto 2020, Piero 2020, NCT 04332666).

This study's investigational product USB002 is pharmaceutically formulated A(1-7), a non-hypertensive derivative of Angiotensin-II (A-II) and is suspended in a vehicle as a sterile solution of USB002 (22.5 mg/ml) which is stable at room temperature for 90 days.

According to the protocol (see Section 4.1 Study Design), this clinical trial includes two parts (dose escalation phase and dose expansion phase). Due to enrolment difficulty to find subjects meeting the study eligibility criteria, in Dec. 2022, the sponsor decided to stop the enrollment and terminate the trial early, when 21 subjects (all Part 1) have been enrolled: 6 subjects in each of the first three cohorts (90, 300 and 600 ug/kg/day) and 3 subjects in Cohort 4, (900 ug/kg/day).

3. Objectives

The objectives of the study are twofold:

- To determine the safety and tolerability of USB002 in treatment of respiratory distress from COVID-19 infection; and
- To identify an early efficacy signal of USB002.

Part 1:

- To determine the maximum tolerated dose (MTD) of USB002 (up to 900 ug/kg/day).

Part 2:

- To determine preliminary efficacy of the USB002 MTD following up to 14 days of continuous infusion.

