5.3. Missing Data

All missing data from CRF will not be imputed. Missing data will be considered missing at random.

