7.4. Analysis Methods

All calculations and analyses will be performed using SAS version 9.4 or higher under the Windows Server 2012R2 operating system at McDougall Scientific Ltd. in Toronto, Canada. Continuous data will be summarized via PROC MEANS - mean, standard deviation, median, range, and 95% CIs, while categorical data will be presented as counts and percentages (or proportions) via PROC FREQ for the descriptive displays.

No statistical inference will be made for all outcomes.

8. Results

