8.2. Primary Outcomes

The primary endpoint of the study will be safety and tolerability, as demonstrated by adverse events (AE), changes in laboratory assessments, ECG assessments, vital signs, and concomitant medications (inotropes and vasopressors). These outcomes will be summarized by cohort. See details in sections 8.2.1 to 8.2.6.

Co-primary endpoint is the difference between USB002 and placebo groups in time to peripheral capillary oxygen saturation (SpO₂) $\geq 94\%$ on room air, sustained for at least 48 hours, through Day 28. All peripheral capillary oxygen saturation (SpO₂) results from baseline to Day 28 will be listed (and summarized if applicable). See section 8.2.7.

No statistical inference will be made for primary endpoint.

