8.2.6. Time to peripheral capillary oxygen saturation (SpO_2) $\geq 94\%$ on room air

The time from baseline to achieving $\text{SpO}_2 \geq 94\%$ on room air will be calculated for each subject. Two summaries will be provided:

- All subjects treated with USB002 vs. all placebo subjects
- USB002 subjects vs. placebo subjects by cohort. That is, comparing between two treatment groups within each cohort (dose level)

All data will be listed.

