8.3.6. Time to hospital discharge

Total days from Day 1 to hospital discharge will be listed and summarized.

8.3.7. Change of OSCI status from Day 1 to Day 28

For each subject, following outcomes will be calculated:

- Days from baseline to the date with OSCI score decreased 1-point from baseline
- Days from baseline to the date with OSCI score decreased 2-point from baseline
- OSCI score change from baseline to Day 28
- Achieving 1-point decrease of OSCI score at Day 28 (Yes/No)
- Achieving 2-point decrease of OSCI score at Day 28 (Yes/No)

These outcomes will be summarized.

All OSCI data will be listed.

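### Time to SpO2 ≥ 94% (co-primary) and time to discharge are null when not reached and no proportion achieving is planned, so the arm summaries describe achievers only; the weaning denominator also contradicts the endpoint definition

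*SAP*

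**What the plan says.** **Status of the endpoint.** SAP 8.2: "Co-primary endpoint is the difference between USB002 and placebo groups in time to peripheral capillary oxygen saturation" reaching at least 94% on room air, sustained for 48 hours, through Day 28.

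**Derivation.** In SAP 7.2 the SpO2 time is "null if the subject did not achieve" the threshold by study termination. The discharge time is "null if the subject was staying in hospital till Day 28". Death in hospital before Day 28 has no code of its own in the discharge row.

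**Missing values and summary statistics.** SAP 5.3: "All missing data from CRF will not be imputed". SAP 7.4: "Continuous data will be summarized via PROC MEANS - mean, standard deviation, median, range, and 95% CIs". The number of contributing subjects is not in that list.

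**Planned output.** SAP 8.2.6 summarises the SpO2 time for all USB002 against all placebo subjects, and then "USB002 subjects vs. placebo subjects by cohort". SAP 8.3.6: "Total days from Day 1 to hospital discharge will be listed and summarized". Neither section specifies the proportion who achieve the event. For OSCI, by contrast, SAP 8.3.7 has Yes/No outcomes at Day 28.

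**Weaning.** SAP 4.3 and Protocol 2.1.2 and 7.2.1 restrict weaning to subjects on MV at baseline. SAP 7.2 sets the outcome to null only for subjects who never used MV between Day 1 and Day 28, and SAP 8.3.3 divides by all subjects who received it.

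**Sample.** SAP section 2 reports 21 subjects, all in Part 1: "6 subjects in each of the first three cohorts (90, 300 and 600 ug/kg/day) and 3 subjects in Cohort 4".

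**The concern.** A mean or median of a null-coded time conditions on having recovered. The two arms then contribute different, outcome-selected subsets, and the comparison is no longer between the randomised groups. If USB002 led more subjects to recover at the same speed, the table would show no difference. If the additional recoverers were later ones, the table would show USB002 as slower. Subjects who die or stay on oxygen disappear from the summary of the co-primary efficacy endpoint.

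The weaning denominator is a different kind of fault: two sections of the SAP define the same proportion over different people. Subjects intubated after baseline enter the result in SAP 8.3.3 but are excluded by the endpoint definition in SAP 4.3.

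**Working it through.** The plan gives no power, recovery rate or event figure for these endpoints, so there is no stated number to reproduce. The enrolment count agrees: 6 + 6 + 6 + 3 = 21. The examples below use **assumed data**. Ten per arm is close to the pooled size (21/2 = 10.5 under 1:1 allocation).

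**1. Who is averaged.** Null when not reached (SAP 7.2), no imputation (SAP 5.3) and PROC MEANS, which ignores nulls (SAP 7.4), together leave only achievers in SAP 8.2.6 and 8.3.6.

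**2. A difference hidden.** Discharged: 6/10 placebo and 9/10 USB002, all on Day 8.
- SAP mean: 48/6 = 8.0 versus 72/9 = 8.0 days.
- n/N: 60% versus 90%.
- Median keeping everyone: the share not yet discharged after Day 8 is 0.4 versus 0.1, so the median is Day 8 in both arms. Only n/N shows the difference here.

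**3. A difference reversed.** Placebo 4/10 on Day 8; USB002 4 on Day 8 and 3 on Day 14.
- SAP mean: 32/4 = 8.0 versus (32 + 42)/7 = 10.6 days.
- n/N: 40% versus 70%.
- Median keeping everyone: the placebo share not recovered stays at 0.6, so the median is not reached. The USB002 share is 0.6 after Day 8 and 0.3 after Day 14, so the median is Day 14.

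**4. How often.** Simulation of 20,000 trials, 10 per arm, recovery probability 60% versus 90%, recovery days uniform on Days 3–16.
- At equal speed, the achievers-only mean is longer on USB002 in 49% of trials. It carries no information on the recovery difference.
- If the additional recoverers fall uniformly on Days 10–16, it is longer on USB002 in 70%.
- By exact binomial calculation, USB002 has more achievers in 92% of trials (ties 6%).

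**5. Within a cohort.** For a planned 3 versus 3 cohort and recovery rate r, the chance that at least one of the 6 subjects drops out of the time summary is 1 − r⁶.

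| r | 1 − r⁶ |
|---|---|
| 0.9 | 47% |
| 0.8 | 74% |
| 0.6 | 95% |

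**6. Weaning denominator.** The error can go either way.
- Five on MV at baseline (2 weaned) and 3 starting later (2 weaned): SAP 8.3.3 gives (2 + 2)/(5 + 3) = 50%; the definition in SAP 4.3 gives 2/5 = 40%.
- Two on MV at baseline (1 weaned) and 3 starting later (none weaned): 1/5 = 20% against 1/2 = 50%.

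**7. Deaths in the MV outcomes.** Protocol 7.2.1 treats death before Day 28 as being on MV. The SAP gives no death rule.
- Progression: 10 not on MV at baseline, 2 progress, 2 die without MV. SAP 8.3.4 as worded gives 2/10 = 20%; the protocol rule gives (2 + 2)/10 = 40%. Those 2 deaths have no first-MV date, so they could not enter time to progression.
- Weaning: 5 on MV at baseline, 2 weaned, 1 of whom later dies before Day 28. The result is 2/5 on the plain definition and 1/5 under the protocol rule.

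**The case against.** **Part 1 is descriptive.** Protocol 7.2.1 says so and leaves the detail to the SAP, SAP 6.1 drops all Part 2 analyses, and SAP 7.4 rules out inference. A reader might infer that omitting the Kaplan-Meier comparison, or leaving it out of the list of changes in SAP section 6, is an undisclosed protocol departure. The documents do not support that. What remains is that a descriptive summary of an arm should still account for the whole arm.

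**The data will be visible.** All SpO2 and discharge data are to be listed, and SAP 8.2 allows SpO2 results to be summarised if applicable. With three per group a listing is arguably the real result. Day 60 mortality and ventilator-free days account for deaths. All of this limits the harm, but no planned table counts the non-achievers.

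**The output may show n.** The SAP refers to a separate ADaM specification, which is not among the documents, and table shells could add n. A displayed n beside the group size would expose the example in step 2 at once. This also lowers confidence that codes for death are truly absent. It does not alter the null rules that SAP 7.2 states.

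**Deaths and MV progression.** A reader might infer that SAP 8.3.4 breaches the protocol's death rule. That rule is attached to Fisher comparisons which the SAP does not perform, and reporting actual progression with deaths shown separately is a legitimate descriptive choice. Only a clarification is needed.

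**OSCI times.** They share the null rule, but SAP 6.2 declares that change and the Day 28 Yes/No outcomes partly offset it.

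**Conclusion.** The point holds for two things. First, as written, the summaries of the co-primary SpO2 time and of time to discharge describe achievers only, with no proportion achieving beside them. Second, the weaning denominator in SAP 7.2 and 8.3.3 contradicts SAP 4.3 and the protocol. Both are worth fixing; neither affects a test or an error rate.

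The size is illustrative. A difference of 60% versus 90% can appear as 8.0 versus 8.0 days, and 40% versus 70% as 8.0 versus 10.6 days. The 70% reversal frequency depends on the additional recoverers being late. A reader might conclude that the trial's actual tables favour one arm. The documents give no recovery data, so the direction of any distortion is unknown.

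**What to change.** 1. **SpO2 and discharge.** Report n/N achieving by Day 28 among all FAS subjects by arm, and for the PP population, counting non-achievers and in-hospital deaths as not achieved. Show any time summary beside n/N, either labelled as 'among achievers' or keeping non-achievers as not reached by Day 28, without p-values. State how subjects with no SpO2 value after discharge or after Day 16 are counted: Protocol 5.4.2 lists Part 1 respiratory assessments only through Day 16, and under 5.4.5 discharged subjects do not return.
2. **Weaning.** Use subjects on MV at baseline as the denominator in SAP 7.2 and 8.3.3.
3. **Deaths before Day 28 (clarification).** State the code for weaning and progression: either follow the rule in Protocol 7.2.1 or declare another in SAP section 6. Under the protocol rule, a subject weaned who then dies before Day 28 changes from Yes to No, so the weaning proportion can change. Show deaths without MV separately from progressors with an MV date, so that the time-to-progression summary matches its count.

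The cost is SAP wording and minor programming, with no new data collection. SpO2 values that were never measured after Day 16 or discharge cannot be recovered, and some medians will read 'not reached'.

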6.2. Time to Achieving 1-point and 2-point OSCI Score Decreases

According to the Protocol, time from Study Day 1 to achieving 1-point and 2-point OSCI decreases will be analyzed using time-to-event method.

Due to the early termination of the study and the small number of subjects in each treatment group, the outcomes will only be summarized descriptively. No time-to-event (Kaplan-Meier) estimates or curves will be provided. See section 8.3.8 for details.

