Achieving 1-point OSCI Decrease at Visit (Yes/No)	= Yes, if OSCI at visit – OSCI at Day 28 (or End of Treatment) ≥ 1 = No, OSCI at visit – OSCI at Day 28 (or End of Treatment) < 1 = null, if OSCI at Day 1 and/or at visit were missing	
Time to Achieving 1-point OSCI decreasing	= Date of first achieving 1-point OSCI decreasing – Study Day 1 + 1 = null if never achieving 1-point decreasing	

Outcome	Calculation	Comment
Achieving 2-point OSCI Decrease at Visit (Yes/No)	= Yes, if OSCI at visit – OSCI at Day 28 (or End of Treatment) ≥ 2 = No, OSCI at visit – OSCI at Day 28 (or End of Treatment) < 2 = null, if OSCI at Day 1 and/or at visit were missing	
Time to Achieving 2-point OSCI decreasing	= Date of first achieving 2-point OSCI decreasing – Study Day 1 + 1 = null if never achieving 2-point decreasing	

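### SAP 7.2 defines a 1- or 2-point OSCI decrease without the baseline score in the subtraction, so the Day 28 responder flag is wrong if programmed as written

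*SAP*

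**What the plan says.** The derivation table in SAP 7.2 has one row for a 1-point and one for a 2-point OSCI decrease at a visit. The conditions for a responder are "Yes, if OSCI at visit – OSCI at Day 28 (or End of Treatment) ≥ 1" and "Yes, if OSCI at visit – OSCI at Day 28 (or End of Treatment) ≥ 2". The No branches use the same subtraction with the inequality reversed. The result is "null, if OSCI at Day 1 and/or at visit were missing".

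Other places describe the same outcome differently:

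- SAP 8.3.7 lists "Days from baseline to the date with OSCI score decreased 1-point from baseline", the matching 2-point item, the OSCI change from baseline to Day 28, and Yes/No flags for a 1- and a 2-point decrease at Day 28.
- Protocol 2.1.2 defines the endpoint as the change in OSCI status from Visit 1/Day 1 to Day 28, reported both as time to change and as proportions with 1- and 2-point changes.
- The general change row in SAP 7.2 is "Value collected at time point (Visit) – Baseline value".
- SAP 6.2 refers to "time from Study Day 1 to achieving 1-point and 2-point OSCI decreases".

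**The concern.** A decrease at a visit should compare the baseline score with the score at that visit. The printed rule compares the visit with a later or simultaneous score (Day 28 or End of Treatment) and leaves baseline out. The rows are also inconsistent within themselves. The null rule names Day 1 and the visit as the two scores needed, yet Day 1 is never used, and the score that is used (Day 28 or End of Treatment) is not covered by the null rule.

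The 1- and 2-point proportions are a named secondary endpoint in the protocol, and SAP 7.1.2 repeats all secondary efficacy endpoints for the per-protocol population. No p-values are planned, so these proportions are themselves what will be reported. A spurious 0% in both arms, or worsening counted as improvement, would mislead the reader of the tables.

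**Working it through.** The plan states no figure on this point to reproduce. The check is to apply the printed rule and compare it with the definition in SAP 8.3.7 and protocol 2.1.2.

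**Inputs.** OSCI runs from 0 to 8, and higher is worse (protocol Appendix 1). In Part 1, Visit 5 is the End of Treatment visit (protocol Table 2, footnote 4). Enrolment stopped at 6 + 6 + 6 + 3 = 21 subjects, all in Part 1 (SAP 2).

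**Formulas**, with k = 1 or 2:

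- Intended: OSCI(baseline) − OSCI(visit) ≥ k
- Printed: OSCI(visit) − OSCI(Day 28 or End of Treatment) ≥ k

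**Flag at Day 28, Day 28 as reference.** OSCI(28) − OSCI(28) = 0 for every score, so neither ≥ 1 nor ≥ 2 can be met. The flag is always No.

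**Flag at Day 28, End of Treatment as reference.** OSCI(28) − OSCI(EoT) ≥ 1 holds only when the Day 28 score is higher, that is worse, than the End of Treatment score. This was checked over all 9 × 9 = 81 score pairs.

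| Day 1 / EoT / Day 28 | Intended: Day 1 − Day 28 | Printed, Day 28 reference | Printed, EoT reference |
|---|---|---|---|
| 5 / 4 / 2 | 5 − 2 = 3: Yes, both flags | 2 − 2 = 0: No | 2 − 4 = −2: No |
| 5 / 4 / 6 | 5 − 6 = −1: No | 6 − 6 = 0: No | 6 − 4 = 2: Yes, both flags |
| 4 / 6 / 8 (death) | 4 − 8 = −4: No | 8 − 8 = 0: No | 8 − 6 = 2: Yes, both flags |

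**Flag at Visit 5.** With End of Treatment as reference, Visit 5 is subtracted from itself and the flag is again always No. With Day 28 as reference, the rule measures change after Visit 5. Scores 5 / 5 / 3 give 5 − 3 = 2, a Yes on both flags at Visit 5, although 5 − 5 = 0 shows no improvement yet. Scores 5 / 6 / 5 give 6 − 5 = 1, a Yes for 1 point, although the subject had worsened by 1. If time to decrease takes its date from this flag, such subjects are dated too early or counted wrongly.

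**All score combinations.** Taking baseline 4 to 7 as an assumption (hospitalised on oxygen or ventilated) and any score from 0 to 8 at Visit 5 and Day 28 gives 4 × 9 × 9 = 324 combinations. By the intended definition, 198 are 1-point and 162 are 2-point responders at Day 28. The printed rule with the Day 28 reference finds 0 in each case. The combinations are not weighted by how likely they are, so these counts show the logic and are not error rates.

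**Scale in this trial.** If all 21 subjects were treated and have a Day 28 score, the rule reports 0 of 21. The documents give no responder rate. If the true 1-point rate were between 30% and 80% (an assumption), 0.30 × 21 = 6.3 to 0.80 × 21 = 16.8, so about 6 to 17 subjects would be miscoded No.

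**The case against.** The best defence is that this is a labelling slip. The subtraction runs from an earlier to a later score, which is the right direction for a decrease ending at Day 28 or End of Treatment. If the word for the visit is read as Day 1, the rule gives the Day 28 result that SAP 8.3.7 wants. That reading shows what was probably meant, but it does not rescue the text. The null rule lists Day 1 and the visit as separate scores, and a flag whose visit is fixed at Day 1 cannot show at which visit a decrease was first reached.

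A second defence is that SAP 7.2 refers to the SDTM and ADaM specifications for the complete calculations. They are not among the documents, so what was programmed cannot be seen. A correct specification would prevent the error, but it would then disagree with the SAP on record.

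Several narrower points stand:

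- SAP 6.2 fixes a time origin and only implies a baseline reference score, so it is weaker evidence of conflict than SAP 8.3.7 and protocol 2.1.2.
- The general change row shows the SAP's own convention. It is not a competing definition of this flag.
- The Day 28 flags in SAP 8.3.7 take their baseline reference from the neighbouring items.
- The 21 is the number enrolled. Subjects without a dose, or with a missing visit score, would drop out of the denominator.
- A wrong flag would sit visibly beside the change score and the listing of all OSCI data.

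**Conclusion.** The rule is wrong as written in both rows. Its null rule, SAP 8.3.7 and protocol 2.1.2 all point to baseline as the reference, and the subtraction does not contain it. Programmed literally with Day 28 as reference, the Day 28 responder proportion is 0% in each arm for both thresholds, with a difference of 0. This holds whatever number of subjects have scores. With End of Treatment as reference, the flag rewards deterioration after treatment.

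The consequence is limited. These are secondary, descriptive proportions in at most 21 subjects, and SAP 7.4 plans no inference. OSCI change from baseline to Day 28 and the other secondary outcomes are untouched, and the time-to-decrease variables are affected only if they use this flag. The wording defect is certain. Whether it reached the output depends on the unseen ADaM specification. It should be corrected because the rule would produce a wrong table and the correction is simple.

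**What to change.** In SAP 7.2, replace the condition in both rows with: Yes if OSCI at baseline − OSCI at visit ≥ 1 (or ≥ 2); No if less; null if either score is missing.

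Take baseline from the SAP's own baseline row, where the "non-missing value closest to the date/time of the first infusion is considered as baseline value". This matters because an OSCI done at screening within 72 hours need not be repeated on Day 1 (protocol 5.4.2 and Table 2, footnote 2). A null rule tied to a Day 1 record could therefore discard subjects who have a usable baseline.

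Remove the End of Treatment alternative from the subtraction. Under the corrected rule End of Treatment is simply another visit at which the flag can be evaluated. If it was meant as a substitute for a missing Day 28 score, the SAP must say so and square it with SAP 5.3, which rules out imputation. Otherwise a missing Day 28 score gives null.

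State in the two time-to-decrease rows that the date is that of the first visit meeting the corrected condition, and confirm that the ADaM specification agrees. Under the corrected rule, 5 / 4 / 2 is a responder on both flags at Day 28 (5 − 2 = 3), while 5 / 4 / 6 and 4 / 6 / 8 are not.

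The cost is two rewritten rows, a clarifying line in two more and a specification check. No new data are needed, and no outcome outside the OSCI responder and time-to-decrease variables changes.
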